#### 2.1.6.3. *Marketing experience in hypertension*

Moreover, the drug is marketed since 1997 by Nippon Chemiphar in Japan and South Korea (Calvan®) to treat hypertension. The cumulative number of patients exposed from July 1997 to February 2021 is estimated to be more than 2,5 million patients, without any change to the safety profile as reported in the successive PSURs and PBRER.

#### 2.2. RISK / BENEFIT ASSESSMENT

#### 2.2.1. Known Potential Risks

Bevantolol is a cardio selective  $\beta$ 1-blocker that is shown to selectively block the positive chronotropic and inotropic action of isoproterenol and is essentially devoid of intrinsic sympathomimetic activity (ISA). It has a mild chronotropic effect at rest and reduces exercise-induced tachycardia and pressor responses. The  $\beta$ 1-blocking effects are almost at the same level as that of metoprolol ( $\beta$ 1-selective blocker), while being slightly weaker than the effect of propranolol ( $\beta$ 1-nonselective blocker).

The safety profile of SOM3355 (bevantolol) in healthy subjects and patients with cardiovascular diseases is well characterized and demonstrated to be safe and tolerable up to 600 mg/day. Therefore, there is no specific reason to suspect that the administration of this compound in non-hypertensive patients can induce clinically relevant complications and in the first trial conducted in HD patients it was well tolerated at doses up to 400 mg/day (see Investigator's Brochure § 7.2). The most frequent AEs during SOM3355 administration in the first Phase 2a study in HD patients were all mild or moderate, did not induce treatment withdrawal, and could be explained by the known effects of the drug such as insomnia, and also bradycardia and hypotension (which are both related to the  $\beta$ 1-blocking effects of bevantolol).

Safety assessments will include monitoring of HR and BP at each visit (measured according to standardized conditions, first in the sitting position and then in the supine and standing positions to detect orthostatic hypotension), and ECG performed at key visits will be assessed with central reading.

Moreover, a wide variety of neuropsychiatric symptoms occur in HD, including, depression, anxiety, irritability, obsessive compulsive behavior and psychosis. Depression is the most common condition

with life time prevalence between 40% and 50% (Du et al, 2013) and suicide rates over five times that found among the general population (Paulsen et al, 2005; Orth et al, 2010, Fahn et al, 2011). Some drugs acting on the dopamine pathway like TBZ have warnings about the risk of aggravation of depression and suicidality. But the differentiation of SOM3355 (bevantolol) in pre-clinical assays with differences in the modulation of the VMATs compared to TBZ may play an important role in the context of the complex involvement of dopaminergic neural pathways in mediating HD prominent psychiatric effects. Therefore, we consider that bevantolol would not induce the same psychiatric effects as they were not reported during the clinical experience of its use in hypertension. However, the risk of depression and suicidality will be carefully assessed along the study with the Beck Depression Inventory scale and the Columbia–Suicide Severity Rating Scale.

The Sponsor is aware that in the current environment, hospitals should preferentially treat subjects with COVID-19 and give priority to trials for the prevention or treatment of COVID-19 infection. This trial will therefore only be initiated at a time when it is ethically and operationally feasible for each of the selected study sites to do so (see Section 8.2). There is currently no known increased risk of contracting COVID-19 as a result of taking the IMP. In addition, study visits will be conducted in such a manner as to ensure patient safety is paramount and to eliminate potential risks of COVID-19 transmission.

#### 2.2.2. Known Potential Benefits

SOM3355 might bring advantages to treat dyskinetic movements related to HD with a better safety profile than similar existing drugs. Currently, the treatment modality for such patients is based on tetrabenazine, a VMAT2 inhibitor which is associated with severe secondary effects, including risk of worsening depression, and suicidal thoughts and behavior in patients with HD. Thus, secondary complications of tetrabenazine treatment nowadays are limiting its clinical benefit in patients suffering from this pathological condition. Such effects were not reported with bevantolol neither during its use to treat hypertension nor in the previous trial in HD. SOM3355 presents a similar VMAT2 inhibitory capacity than the reference compound tetrabenazine but with different binding properties leading to its differentiation in monoamines signaling and also a specific binding to VMAT1 receptors that may explain its different safety profile. The previous Phase IIa study conducted with SOM3355 in HD patients showed that more than half of the patients had an improvement of their chorea symptoms measured by a reduction of at least 2 points in the TMC score with SOM3355 compared to placebo, and some patients had even greater improvements, while no neuropsychiatric symptoms were reported.

#### 2.2.3. Assessment of Potential Risks and Benefits

Patients could benefit from treatment with SOM3355, which is known to reduce chorea symptoms as shown in the previous Phase 2a study, and it will be assessed as the primary endpoint.

SOM3355 is a well-known drug which has proven its good safety profile since more than 25 years of use as hypertensive drug. It has no warning regarding neuropsychiatric side effects and it was also well tolerated in the previous trial in HD patients, with no worsening of depression or suicidality although the sample was very limited.

Safety will be carefully monitored along the trial, particularly the risk of depression and suicidality will be assessed at each visit by the physician through specific scales (Beck Depression Inventory and Columbia-SSRS). Patients with known depression should be treated and stabilized with antidepressant therapy. Patients with severe untreated or under-treated depression at screening, or presenting a risk of suicide (item on suicidality >0 in BDI scale) are excluded from this study, and if the risk of suicide arises during the trial the patient should be immediately withdrawn from the study.

The known effect of bevantolol as beta blocker may induce potential side effects such bradycardia or orthostatic hypotension. Patients with a history of, or current, hypotension or bradycardia (HR <50 bpm) at the screening will be excluded from the study. Hemodynamic parameters (HR and BP) will be carefully monitored during the study as well as the recording of ECG to assess any abnormality. Severe permanent bradycardia will be excluded.

#### 2.3. STUDY RATIONALE

*In vitro*, SOM3355 provided functional inhibition of the VMAT2 with similar potency to that of TBZ but different binding properties that may provide a change in monoamine signaling improving the chorea symptoms of HD with less risk of severe side effects. Relying on its VMAT2 inhibition activity, and good tolerability at doses from 100 to 600 mg/day administered once or twice daily (OD or BID), SOM Biotech is now developing SOM3355 for the treatment of the dyskinetic movement disorders related to HD.

The first Proof of Concept Phase 2 study (SOMCT02) assessing SOM3355 in HD patients is suggestive of its clinical effect on chorea. PK-PD analysis assessed the relationship between plasma levels of SOM3355 and the absolute reduction of TMC score with a linear model. Dose proportionality was shown and modelling allowed us to predict that plasma concentration values around 3000 ng/ml will induce a mean reduction of TMC score of at least 3.0 points compared to placebo. Assuming the dose proportionality, an increase of the dose to 300 mg BID (600 mg/day) would be required in the next trial to obtain such improvement in TMC score and therefore substantial decrease of chorea symptoms that could be comparable to the TBZ effect.

#### 3. OBJECTIVES AND ENDPOINTS

#### 3.1. OBJECTIVES OF THE STUDY

The primary objective of the study is to assess the efficacy of two doses of SOM3355 (400 mg/day and 600 mg/day taken twice daily [BID] over at least 8 weeks at maintenance dose) compared to placebo to reduce chorea in HD patients, measured by the change in TMC score (primary efficacy endpoint).

Secondary objectives of the study are:

To evaluate the safety and tolerability of two doses of SOM3355 (400 mg/day and 600 mg/day taken BID) compared with placebo in HD patients, with particular attention to depression and suicidality and to the cardiovascular hemodynamic parameters.

And to evaluate the efficacy of the two doses of SOM3355 (400 mg/day and 600 mg/day taken BID) compared with placebo on:

- the change of Clinical Global Impression (CGI-C),
- o the change of Patient Global Impression (PGI-C),
- o the percentage of responders based on the improvement  $\geq 2$  in TMC score,
- o the percentage of change of TMC score.

A PK sub-study in a subset of 24 patients will allow to determine the PK profile of the two doses of SOM3355 (200 mg and 300 mg given twice per day) at steady state and to model PK-PD assessments of hemodynamic and cardiac parameters.

#### 3.2. PRIMARY EFFICACY ENDPOINT

The primary measure of efficacy will be the change in TMC sub-score of the UHDRS® between baseline and end of maintenance dose (the mean of Visit 4 and Visit 5 minus the mean of Visit 0 and Visit 1).

The TMC score is a standardized, reliable chorea assessment based on frequency and severity in 7 body regions.

#### 3.3. SECONDARY EFFICACY ENDPOINTS

Key secondary efficacy endpoint:

• Change from baseline in Clinical Global Impression (CGI-C),

Other secondary efficacy endpoints:

- Change from baseline in Patient Global Impression (PGI-C).
- TMC-response defined as improvement ≥2 in TMC score between baseline and end of

maintenance dose.

- Percentage of change in TMC score between baseline and the end of maintenance dose.
- Change from baseline in Total Motor Score (TMS) of the UHDRS®.
- Change from baseline in Gait sub-score of the UHDRS®.
- Change from baseline in Dystonia sub-score of the UHDRS®.
- Change from baseline in EQ5D-5L measuring quality of life.

#### 3.4. SAFETY ENDPOINTS

Safety assessments will include the following:

- Incidence, frequency, and severity of AEs in each treatment group.
- Change from baseline in:
  - Vital signs: BP, including orthostatic BP, and HR.
  - ECGs.
  - Clinical laboratory test results (chemistry, hematology).
  - Physical examination findings, weight.
  - C-SSRS assessing suicidality.
  - BDI scale assessing depression.
  - ESS assessing sleepiness.
  - TFC of the UHDRS® assessing functioning.
  - Functional Assessment of the UHDRS®.
  - BARS assessing akathisia.
  - MoCA scale to assess cognitive disturbances.
  - PBA-s to assess behavioral symptoms in HD.

#### 3.5. PK-PD ASSESSMENTS

**SOM3355 plasma concentration** will be measured at each visit under treatment with SOM3355 (i.e. Visit 2 to Visit 5) in all patients. Plasma samples will be collected pre-dose (before the dug intake) and 2 hours after the drug intake (corresponding to the expected  $T_{max}$ ) at Visit 2 and Visit 4, and only pre-dose at all other visits (Visit 3 and Visit 5).

**Prolactin plasma level** will be measured at each visit from Visit 1 to Visit 6 in all patients. Plasma samples will be collected pre-dose (before the dug intake) and 2 hours after the drug intake (at  $T_{max}$ ) at Visit 2 and Visit 4, and only pre-dose at all other visits (Visit 1, Visit 3, Visit 5 and Visit 6).

#### 4. STUDY DESIGN

#### 4.1. OVERALL DESIGN

This is an international, multicenter, double-blind, randomized, placebo-controlled, parallel-group Phase IIb study assessing two doses of SOM3355 (400 or 600 mg/day), taken as 200 mg BID or 300 mg BID, in patients presenting choreic symptoms related to HD.

The study will enroll 129 patients with a genetically-proven diagnosis of Huntington's Disease (confirmed by HTT gene CAG repeats ≥36), of mild to moderate severity (TFC score ≥7) with choreic symptoms (TMC score ≥10). The patients will be recruited in investigating sites in various European countries. Ambulatory patients will be recruited by reference centers for HD in collaboration with patient advocacy groups and the EHDN.

Patients who meet all of the eligibility criteria will be randomized at Visit 1 in a 1:1:1 ratio to one of the 3 treatment arms to receive either SOM3355 400 mg/day, SOM3355 600 mg/day, or placebo, all given BID. Dosing will start with an up titration in the first 3 weeks and will then be maintained at a fixed dose for 7 weeks. After 10 weeks, patients will down titrate to 1 capsule a day of study drug for 1 week, followed by 1 capsule a day of placebo to assess the effect of drug interruption.

The overall study duration is 12 weeks plus 1 or 2 weeks for screening.

Screening period (1 or 2 weeks before inclusion, from Visit 0 to Visit 1): patients will undergo an independent evaluation by a qualified healthcare provider to determine their capacity to provide informed consent and their eligibility according to the study selection criteria. After informed consent is obtained, patients who are stable from a medical and psychiatric standpoint will undergo a screening evaluation to confirm their eligibility. The evaluations performed at Visit 0 and Visit 1 will be used as baseline to assess the treatment effect.

**Randomization (at Visit 1):** patients who fulfil all selection criteria at the end of the screening period will be randomized and will initiate therapy with either SOM3355 or placebo.

**Up-Titration period (between Visit 1 and Visit 2):** patients will start the active treatment with an up-titration period of 3 weeks. They will be instructed to take one capsule every day in the morning during the first week, and then two capsules, one in the morning and one in the evening every day from the second week.

- Patients allocated to 400 mg/day treatment arm will receive 200 mg once daily (OD) the first week, and then 200 mg BID the second and third week.
- Patients allocated to 600 mg/day treatment arm will receive 200 mg OD the first week, 200 mg
   BID the second week, and then 300 mg BID the third week.
- Patients allocated to the placebo arm will take matching placebo capsules according to the same pattern, once a day during the first week and twice per day from the second week.

**Maintenance dose (from Visit 2 to Visit 5)**: the dose reached in each arm (200 mg BID or 300 mg BID or placebo) will be maintained for 7 additional weeks. At the end of this maintenance dose period, two evaluations will be performed one week apart, at Visit 4 (end of Week 9) and at Visit 5 (end of Week 10), to assess the treatment effect versus baseline.

End of study with 1-week down-titration and 1-week placebo washout (from Visit 5 to Visit 6): during the last 2 weeks (Week 11 and Week 12), the patients will be instructed to take only 1 capsule in the morning. The two arms receiving the active drug will be dispensed capsules dosed at 200 mg for one week to decrease the dosing to 200 mg/day. During the last week, all the patients will receive capsules of placebo.

Patients will return for a last visit (Visit 6) to assess the withdrawal of the drug.

#### 4.2. PK SUB-STUDY

A PK sub-study will be conducted to characterize the PK profile of repeated doses of SOM3355 at 400 and 600 mg/day. This analysis will be performed by collecting 12-hour PK samples (H0, H0.5, H1, H1.5, H2, H3, H5, H8, and H12) in 8 patients per arm (24 patients in total) that will be hospitalized for 24 hours at Visit 2. These patients will be recruited by 3 or 4 sites able to manage the logistics of PK sampling.

PK data from this sub-study will be collected in an independent database and analyzed by an independent un-blind central laboratory before the end of the clinical trial. The results will be given in a blinded manner until the final data lock.

In addition, cardiac and hemodynamic parameters will be collected in parallel, with 12-hour cardiac Holter and blood pressure measurements before each PK sample, to allow PK-PD modeling assessments.

#### 4.3. RATIONALE FOR STUDY DESIGN

This 12-week Phase 2b study is designed to evaluate in parallel groups the efficacy, safety and tolerability of two doses of SOM3355 (400 mg/day or 600 mg/day, taken either as 200 mg or 300 mg BID) compared with placebo in HD patients with chorea. A previous Phase 2a study (SOMCT02) has already tested the effect of 400 mg/day SOM3355 (given as 200 mg BID) compared with placebo in a crossover design on 6-week periods, and it has shown a reduction of choreic symptoms measured by a significant decrease of the TMC score, and a good tolerability at the tested dose. For this Phase 2b trial, the regulatory authorities recommended a dose-finding study testing different fixed doses in parallel compared with placebo, to correctly assess the dose effect and determine the best dose to be tested in Phase 3.

It is deemed prudent to initiate the treatment by escalating the dose with weekly increases (200 mg OD the first week and 200 mg BID the second week to reach 300 mg BID on the third week for the patients allocated to the 600 mg/day treatment arm) for better tolerability and to reduce the risk of hypotension or bradycardia at the start of treatment. Then, the reached dose (400 mg/day or 600 mg/day) will be maintained for 7 additional weeks.

At the end of the maintenance dose, the study drug is down-titrated for one week (at 200 mg/day) to avoid an abrupt interruption of the dose, followed by a 1-week placebo washout period to assess the effect of the interruption of the study drug.

#### **4.4. JUSTIFICATION FOR DOSE**

The proposed clinical doses are within the dose range studied in the nonclinical program, and the lowest observed adverse effect level (LOAEL) in dogs corresponds to the calculated human equivalent dose (HED) of 1500 mg (see Investigator's brochure § 5.3.2).

The selected doses of 400 mg/day and 600 mg/day taken BID (i.e. 200 mg BID and 300 mg BID) have already been used in previous clinical trials.

Bevantolol in doses up to 600 mg/day has been studied during the clinical development of the drug for the treatment of hypertension and angina pectoris (Maclean et al, 1988; Al.Khawaja et al, 1986). Notably in a randomized trial comparing bevantolol to propranolol in hypertension, 39 patients received the dose of 200 mg BID and 47 patients received the dose of 300 mg BID for a 6-month double-blind period after a 6-week double blind titration period. These doses were well tolerated during this long term therapy.

The previous Phase 2a study in HD (SOMCT02) studied the effect of 400 mg/day SOM3355 (given as 200 mg BID) compared with placebo in a crossover design given for 6 weeks of dosing. The study showed good tolerability and safety of SOM3355 dosed at 200 mg BID in patients with HD. Moreover, in this study, PK-PD assessments have shown dose linearity of plasma concentrations, consistent with the previous published data (Latts et al, 1986), and the relationship between plasma levels of SOM3355 and the absolute reduction of TMC score analyzed with a linear model allowed us to predict that the dose of 300 mg BID would provide plasma concentration values that may induce a mean reduction of TMC score of at least 3 points compared to placebo and therefore substantial decrease of choreic symptoms that could be comparable to TBZ effect.

#### 4.5. END OF STUDY DEFINITION

A patient is considered to have completed the study if he/she has completed all visits of the study. The end of the study is defined as the date of the last visit of the last patient in the study.

#### 5. STUDY POPULATION

#### 5.1. INCLUSION CRITERIA

Eligibility criteria to participate in this study are:

- 1. Males or females  $\geq 21$  years old.
- 2. Patients with a diagnosis of Huntington's Disease determined by a movement disorders expert and confirmed by a number of HTT gene cytosine-adenosine-guanine (CAG) repeats ≥36.
- 3. UHDRS® Total maximal chorea (TMC) score ≥10
- 4. UHDRS® Total Functional Capacity (TFC) ≥7 (corresponding to mildly to moderately impaired patients).
- 5. Able to walk independently or with minimal assistance.
- 6. Females of child-bearing potential must use a medically accepted effective method of birth control, agree to continue this method for the duration of the study and for at least 1 month following the last dose of study drug, and be negative to serum pregnancy test performed at the screening visit (Refer to section 5.4 for complete advice on contraception requirements of this study). Female patients should not be breast-feeding.
- 7. In the opinion of the Investigator, the patient must have adequate support to comply with the entire study requirements as described in this protocol (e.g. transportation to and from the trial site, self-rating scales, drug compliance, scheduled visits, etc.).
- 8. Able and willing to provide written informed consent prior to any study-related procedure being performed at the screening visit.

#### 5.2. EXCLUSION CRITERIA

Patients are excluded from the study if any of the following criteria apply:

- 1. Onset of HD symptoms prior to age of 21 years, corresponding to juvenile forms of HD.
- 2. HD patients presenting rigid akinesia.
- 3. Use of other vesicular monoamine transporter type 2 (VMAT2) inhibitors such as tetrabenazine, deutetrabenazine, or valbenazine within 3 months before enrollment, and at any time during the study period; and use of other antichoreic treatment such as any neuroleptic within 2 months or amantadine, memantine, riluzole within 1 month before enrollment and along the study.
- 4. Patients who experienced severe depression or suicide attempt in the last 5 years.
- 5. Severe untreated or under-treated psychiatric illness such as active suicidal ideation or behavior (BDI-21 item #9 >0 and active suicidal ideation in C-SSRS) or depression at screening or baseline (BDI-21 items total score >30); although patients taking authorized antidepressant therapy at a stable dose for at least 2 months and stabilized can be enrolled.

- 6. Patients with a history of, or current, hypotension (SBP <110 mmHg) or bradycardia (HR <50 bpm), and patients with known orthostatic hypotension as defined by the European Society of Hypertension (reduction in SBP ≥20 mmHg or in DBP ≥10 mmHg).
- 7. Patients with hypertension already treated with more than 2 antihypertensive drugs.
- 8. Other active clinically significant illness, including unstable cardiovascular disease, angina pectoris, congestive heart failure, pulmonary hypertension, peripheral arterial disease, history of pheochromocytoma, asthma, COPD, diabetic ketoacidosis or metabolic acidosis, or neoplastic pathology, which could interfere with the study conduct, or counter-indicate the study treatment, or to place the patient at risk during the trial, or compromise their study participation.
- 9. Any significant serious abnormality in the electrocardiogram (ECG), e.g. recent myocardial infarction, severe sinus bradycardia (<50 bpm), atrioventricular block (grades I to III, with PR >240 msec), sinoatrial block, atrial sinus disease or prolonged QTc interval at screening (ECG Bazett's corrected QT interval (QT /√ [HR/60] >450 msec for males or >470 msec for females), or a known history of long QTc syndrome.
- 10. Patients with severe hepatic impairment, or with severe renal impairment, or with any other significant abnormality in the physical examination or clinical laboratory results that, in the Investigator's opinion, would not be compatible with study participation or represent a risk for the patient while in the study.
- 11. Females who are pregnant or lactating, or who intend to become pregnant during the study period.
- 12. Patients with allergy under desensitization, with known psoriasis, or a known allergy / hypersensitivity to any ingredients of the trial medication or placebo.
- 13. History of alcohol or substance abuse in the previous 12 months.
- 14. Patients participating in any other study, and the use of any investigational therapy, within the 1month prior to entry in this study.

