Exclusion criteria	Patients are excluded from the study if any of the following criteria apply:  1. Onset of HD symptoms prior to age of 21 years, corresponding to juvenile forms of HD.
	2. HD patients presenting rigid akinesia.
	3. Use of other vesicular monoamine transporter type 2 (VMAT2) inhibitors such as tetrabenazine, deutetrabenazine, or valbenazine within 3 months before enrollment, and at any time during the study period; and use of other antichoreic treatment such as any neuroleptic within 2 months or amantadine, memantine, riluzole within 1 month before enrollment and along the study.
	4. Patients who experienced severe depression or suicide attempt in the last 5 years.
	5. Severe untreated or under-treated psychiatric illness such as active suicidal ideation or behavior (BDI-21 item #9 >0 and active suicidal ideation in C-SSRS) or depression at screening and/or initiation visit (BDI-21 items total score >30); although patients taking authorized antidepressant therapy at a stable dose for at least 2 months and stabilized can be enrolled.
	6. Patients with a history of, or current, hypotension (SBP <110 mmHg), bradycardia (HR <50 bpm), or orthostatic hypotension as defined by the European Society of Hypertension (reduction in SBP ≥20 mmHg or in DBP ≥10 mmHg).
	7. Patients with hypertension already treated with more than 2 antihypertensive drugs.
	8. Other active clinically significant illness, including unstable cardiovascular disease, angina pectoris, congestive heart failure, pulmonary hypertension, peripheral arterial disease, history of pheochromocytoma, asthma, COPD, diabetic ketoacidosis or metabolic acidosis, or neoplastic pathology, which could interfere with the study conduct, or counter-indicate the study treatment, or to place the patient at risk during the trial, or compromise their study participation.
	9. Any significant serious abnormality in the electrocardiogram (ECG), e.g. recent myocardial infarction, significant sinus bradycardia (<50 bpm), atrioventricular block (grades I to III with PR >240msec), sinoatrial block, atrial sinus disease or prolonged QTc interval at screening (ECG

Bazett's corrected QT interval (QT  $/\sqrt{[HR/60]}$  >450 msec for males or >470 msec for females), or a known history of long QTc syndrome.

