# 5.7. PATIENT WITHDRAWAL CRITERIA

In accordance with the Declaration of Helsinki, patients will be free to withdraw from the study at any time if they wish to do so, for any reason specified or unspecified. Such withdrawal should not affect the required and provided medical care.

In addition, the Investigator may interrupt the patient participation from the study at any time if he/she considers it necessary for any reason including:

- Pregnancy.
- Ineligibility (either arising during the study or retrospective having been overlooked at screening).
- Significant protocol deviation.
- Significant non-compliance with treatment regimen or study requirements.
- An AE which requires discontinuation of the study medication or results in inability to continue to comply with study procedures, particularly if the patient presents a **severe depression** (BDI-21 item total score ≥30), or **suicidal ideation or behavior** (BDI-21 Item #9 >0 and active suicidal ideation in C-SSRS), or **severe hypotension** (SPB/DBP <90/60 mmHg), or **orthostatic hypotension** as defined by the ESH, or **sustained un-tolerated bradycardia** (HR <50 bpm).
- Consent withdrawn.
- Lost to follow-up.
- The Investigator or Sponsor determines it is in the best interest of the subject to discontinue the patient's participation in the study.

Patients who discontinue study treatment or active participation in the study will no longer receive study treatment but will be followed for safety. When a patient withdraws from the study, the reason(s) for withdrawal shall be recorded by the Investigator on the relevant page of the eCRF. Whenever possible, all patients who discontinue study treatment or withdraw from the study prematurely will undergo all end-of-treatment assessments. Patients who fail to return for final assessments will be contacted by the site staff. Following a minimum of 2 documented unsuccessful telephone calls, a registered letter will be sent to the patient in a final attempt to ensure protocol compliance.

It is vital to obtain follow-up data on any patient withdrawn because of an AE or SAE. In every case, efforts must be made to undertake protocol-specified, safety, follow-up procedures.

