## 7.3.6. Beck Depression Inventory (BDI)

The BDI scale is currently one of the most widely used instruments in both research and clinical practice for assessing depression, with good reliability and validity, which can be used to document changes brought by therapy. Created by [name] in 1961, and revised in 1996 (BDI-II) for more consistency with the revised DSMIV, it is a 21-question multiple-choice self-report inventory. The questionnaire is composed of items relating to symptoms of depression such as hopelessness and irritability, cognitions such as guilt or feelings of being punished, as well as physical symptoms such as fatigue, weight loss, and lack of interest in sex (Wang , 2013).

Each item has four possible degree of severity rated from 0 to 3, and the patient is asked to choose the one that is closest to how he/she feels. The 21 items are summed linearly to create a score which ranges from 0 to 63. It can be administered as an interview by the clinician or as a self-report instrument.

The suicide item #9 includes the following:

- 0. "I don't have any thoughts of killing myself."
- 1. "I have thoughts of killing myself, but I would not carry them out."
- 2. "I would like to kill myself."
- 3. "I would kill myself if I had the chance."

Total Score Levels of depression (Beck et al, 1988):

- 0 to 9: No depression or minimal depression
- 10 to 18: Mild to moderate depression
- 19 to 29: Moderate to severe depression
- 30 to 63: Severe depression

BDI will be assessed at each visit.

A total score of BDI-21 items  $\ge$ 30 or item 9 >0 results in an exclusion of the patient from further participation in the study.

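### The BDI entry limit (>30) is one point looser than the protocol's own exit rule and severe-depression band (≥30), so a score of exactly 30 passes the number at entry but already meets the rule for leaving

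*Protocol*

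**What the plan says.** **Entry.** Exclusion 5 in Protocol section 5.2 excludes "depression at screening or baseline (BDI-21 items total score >30". The synopsis (section 1.1) words the timing differently but uses the same operator: "depression at screening and/or initiation visit (BDI-21 items total score >30". The criterion opens in general terms, "Severe untreated or under-treated psychiatric illness such as active suicidal ideation or behavior", and closes with an allowance: "although patients taking authorized antidepressant therapy at a stable dose for at least 2 months and stabilized can be enrolled".

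**Exit.** Section 7.3.6 states that a BDI total of 30 or more, or a score above 0 on item 9, "results in an exclusion of the patient from further participation in the study". Section 5.7 lists severe depression, given as "BDI-21 item total score ≥30", among the adverse-event reasons for which the investigator may stop a patient's participation. Section 5.7 is discretionary; 7.3.6 is worded as a consequence.

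**Severity bands.** Protocol section 7.3.6 and SAP section 4.10.8 both class totals of 30 to 63 as severe and 19 to 29 as moderate to severe.

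**Other entry wording without a BDI total.** Exclusion 4 bars "Patients who experienced severe depression or suicide attempt in the last 5 years". Section 4.1 sends into screening only "patients who are stable from a medical and psychiatric standpoint". Section 2.2.3 says that severe depression left untreated or under-treated at screening is a reason for exclusion. None of the three gives a BDI-total cut-off.

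**Timing.** The BDI is completed at every visit, including Visit 0 and Visit 1 (Table 1; sections 8.1.1 and 8.1.2). Section 8.1.2 has the investigator re-check all eligibility criteria at Visit 1, before randomization.

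**The concern.** Entry and exit limits need not be equal. When they differ by design, however, one expects entry to be the stricter, so that an enrolled patient has some room before the exit rule applies. Here entry is the looser of the two, by one point, and the protocol gives no reason for it. The exit rule, the withdrawal criterion and both severity tables agree on 30 as the start of severe depression. Only the entry limit departs from them.

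For a patient who scores 30 at Visit 0 or Visit 1, the numeric limit does not exclude and section 7.3.6 does. The decision then depends on which section the site follows, or on clinical judgement under criteria that have no number, and two sites could treat the same score differently. A patient randomized at 30 and then removed under 7.3.6 would be an avoidable withdrawal.

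Depression and suicidality are a named safety focus of the trial (section 3.1; SAP section 1.2), and section 2.1.2 notes that the approved drugs of this mechanism are contraindicated in severe or inadequately treated depression. The entry number should not sit one point inside the protocol's own severe band.

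**Working it through.** No sample-size or power formula is involved. The check compares the operators on the scale.

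**Inputs**
- Scale: 21 items scored 0 to 3 and summed, so the total is a whole number from 0 to 63 (section 7.3.6). That is 63 − 0 + 1 = 64 possible totals, and 30 is one of them.
- Entry limit: excluded if total > 30 (section 5.2 and synopsis, exclusion 5).
- Exit rule: participation ends if total ≥ 30 (section 7.3.6).
- Severe band: 30 to 63 (section 7.3.6; SAP section 4.10.8).

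**Rules side by side**

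| BDI total | Excluded by entry limit (>30)? | Meets 7.3.6 exit rule (≥30)? | Severe band? |
|---|---|---|---|
| 0–29 | No | No | No |
| 30 | **No** | **Yes** | **Yes** |
| 31–63 | Yes | Yes | Yes |

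**Size of the gap**
- Scores in the severe band: 63 − 30 + 1 = 34.
- Scores caught by >30: 63 − 31 + 1 = 33.
- Severe scores missed: 34 − 33 = 1, namely 30.
- With ≥30 at entry: 34 of 34 caught, 0 missed.

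**The antidepressant allowance.** Exclusion 5 does not say whether its closing allowance qualifies the BDI limit or only the general wording on psychiatric illness, and 7.3.6 has no matching exception. The table counts the scores that pass the numeric entry limit yet meet the exit rule under each reading.

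| Reading | Patients | As written | With ≥30 |
|---|---|---|---|
| A: allowance does not override the limit | All | 1 | 0 |
| B: allowance overrides the limit | Treated and stabilised | 34 | 34 |
| B: allowance overrides the limit | All others | 1 | 0 |

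Under reading A the change of operator closes the gap completely. Under reading B it closes it for everyone except treated, stabilised patients, for whom it closes 0 of 34.

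**Number of patients.** The documents give no distribution of BDI totals in the target population, so the expected number scoring exactly 30 at Visit 0 or Visit 1 cannot be calculated.

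**The case against.** The strongest reply is that exclusion criteria are cumulative bars: escaping one number is not an instruction to enrol. If 7.3.6 applies at Visits 0 and 1, where the BDI is also scored, the stricter rule already keeps the patient out. If it applies only on study, the two rules do not collide at entry and all that remains is a one-point offset. Exclusion 4 also bars severe depression in the last 5 years, and the only BDI meaning the protocol attaches to severe is 30 to 63, so a site could exclude a current score of 30 by that route. The BDI and the C-SSRS are repeated at every visit, which limits any harm.

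Much of this stands as a limit on the consequence, and it is why the point is minor. It does not remove the inconsistency. If 7.3.6 governs screening, the protocol holds two different BDI cut-offs for the same assessment. If it governs only the period after entry, a patient can be admitted at a score that would end participation if it were repeated at the next visit. Exclusion 4, section 4.1 and section 2.2.3 carry no BDI number, so using them to exclude a score of 30 is a matter of judgement that may vary between sites.

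Reading B can fairly be called strained. The allowance requires the patient to be stabilised, section 4.1 asks for psychiatric stability, and exclusion 4 has no antidepressant exception. A very high score would be hard to square with that wording. The figure of 34 is therefore the outer bound of an ambiguous clause, not an expectation.

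It is also true that changing the operator does not fully reconcile the two sections. Exclusion 5 and section 5.7 require both item 9 above 0 and active ideation on the C-SSRS, whereas 7.3.6 acts on item 9 alone. That is a separate discrepancy from the BDI-total limit.

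**Conclusion.** The concern holds. The numeric entry limit on the BDI total is one point looser than the exit rule in section 7.3.6, and it leaves out the lowest score that the protocol and the SAP both class as severe. The mismatch is exactly one score, 30, out of 64, with 33 of the 34 severe scores covered as written.

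This rests on two things: the total is a whole number, which follows from the scoring, and the antidepressant allowance does not override the limit. If it does override it, the edit leaves the gap unchanged for treated, stabilised patients.

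Severity is minor. Probably very few patients would score exactly 30 at Visit 0 or Visit 1, although the documents do not allow a count. Judgement-based criteria can still exclude them, and monitoring is repeated at each visit. The planned power, sample size and alpha are unaffected.

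**What to change.** Replace >30 with ≥30 for the BDI total in exclusion 5, in both section 5.2 and the synopsis. This brings the entry number into line with sections 5.7 and 7.3.6 and with the severity bands in the protocol and the SAP; the SAP itself needs no edit.

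In the same amendment, add one sentence to exclusion 5 stating whether a patient stabilised on an authorized antidepressant is still subject to the BDI limit. If the allowance is meant to override it, section 7.3.6 needs a matching exception; otherwise such a patient could enter and at once meet the exit rule.

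The text change is one character in two places plus a clarifying sentence, but it has to go through a protocol amendment under section 10.4. In recruitment, the cost is the patients who score exactly 30 at Visit 0 or Visit 1 and would now meet the numeric exclusion, probably very few. For those stabilised on antidepressants, whether they become screen failures depends on how the allowance is clarified.
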